Globally, pneumonia accounts for 16% of all deaths of children under 5 years oldⁱ. In sub-Saharan African (SSA) countries it causes approximately 750 000 child deaths per year in. In Mali, about 900,000 pneumonia episodes occur in children under 5 years of age annually, leading to almost 8,000 deaths. Pneumonia accounts for 2% of under-five deaths in Mali, but only 38% of children under five presenting with symptoms of pneumonia are taken to an appropriate health provider. In line with the World Health Organization (WHO) guidelines, increasingly, the first point of contact with the health care system for people seeking care for pneumonia symptoms is through community health care workers (CHWs)ⁱⁱⁱ. Aware that access to accurate diagnosis, treatment and appropriate referral determines a child's survival the Mali Ministry of Health (MoH) introduced Integrated Community Case Management (iCCM) in 2007, authorizing community health workers (CHWs) to diagnose and treat pneumonia, malaria, diarrhoea and malnutrition in children under five. Research has suggested that community case management of pneumonia, if properly implemented, could reduce under-five deaths from pneumonia by 70% v.

In 2012, WHO and UNICEF published a joint statement that supported iCCM as "an essential strategy that can both foster equity and contribute to sustained reduction in child mortality" and identified fast breathing as the key presenting symptom for diagnosing and treating pneumonia using the iCCM strategy i. WHO has set the threshold for respiratory rate (respiratory rate per minute) in infants less than 2 months at a respiratory rate of 60 per minute, for children 2 to 12 months at a respiratory rate of 50 per minute and for children 1 to 5 years at a respiratory rate of 40 per minute in its Integrated Management of Childhood Illness (IMCI) handbook widely used as the technical guidelines at the community level of care iii. Studies demonstrate that there is evidence to show that, when well-trained, CHWs can adequately manage pneumonia cases at the community level ix. However, when training is deficient CHWs' skills in measuring respiratory rates and accurately classifying pneumonia remain a challengex xi xii.

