In Mali, as part of their basic training, CHWs are trained to detect suspected pneumonia cases using video, practice sessions and their basic training manual. Algorithms used for diagnosis developed in the 1980s include assessing danger signs in children with a cough, counting respiratory rates, and observing chest in drawing to classify respiratory illness^{xiii}. These algorithms correspond with WHO's definition of presenting symptoms for pneumonia: cough and/or difficult breathing, with or without fever, the presence of either fast breathing or lower chest wall in-drawing where the child's chest moves in or retracts during inhalation.^{xiv} Because counting respiratory rate by observing the chest, by using a stethoscope or putting one's hand on an abdomen has been shown to have conflictive results^{xv}, both WHO and UNICEF recommend respiratory rate timers (RRTs) as a CHW diagnostic tool for pneumonia at the community level. There are several studies that have demonstrated that these tools can be used successfully by CHWs trained to use them^{xvi}. However, study results cautioned that for CHWs to be able to easily and accurately classify pneumonia cases additional practice in counting respiratory rates and simple job aides would be necessary^{xviii} x^{viii}.

Pneumonia is the number one cause of under-five deaths in Mali and case fatality rates can exceed 20%, but in 2013, of the 231,548 reported pneumonia cases only 20% were treated by CHWs. The quality of community health workers' diagnostic skills can influence how communities accept and use these workers. Poor competency in CHWs to correctly count respiratory rate, a key indicator for pneumonia detection, puts CHWs and their patients at risk of frequently misdiagnosing pneumonia and over prescription of antibiotics. The need for strong CHW competency to correctly count respiratory rate for a quick and accurate detection of pneumonia is evident.

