The challenge for many countries implementing iCCM is a lack of funding to provide consistent supervision, refresher courses and feedbacks, putting at risk the populations CHWs are placed to serve. In 2014, only 63% of routine supervisory visits to assess CHW skills in Mali were reported to be completed xix. Supportive supervision has been a continuous reported gap in ICCM and studies have demonstrated the correlation between strong supervision and improved CHW performance xi xi. Research shows that the access to mHealth tools, for CHWs working in remote areas and having access to consistent training and supervision, can help improve the effectiveness of the services they provide xii.

Royal Philips' 2015 pledge to Every Woman, Every Child includes improved pneumonia diagnosis and treatment in low resource countries. To this end, Phillips invented the Children's Automated Respiratory Monitor (ChARM), a low cost device for low skilled health workers. Clinical tests have concluded that ChARM is an acceptable alternate diagnostic tool for identifying fast breathing among <5 children, which may have potential for use at point-of-care by low-skilled community health workers in low resource countries xxiii The proposed study will test whether or not the Children's Automated Respiratory Monitor (ChARM) can be successfully used as a tool to help CHWs self-monitor and improve their competency to count respiratory rate accurately, diagnose pneumonia cases correctly and determine whether to treat or refer a child under 5. By applying the ChARM device on the child, and at the same time counting the child's respiratory rate themselves, the CHWs can carry out an accurate real time assessment of their breath counting skills. This randomized cluster trial will evaluate ChARM's potential as a teaching/monitoring tool to support CHWs skill improvement in the diagnosis and treatment of children under 5 with symptoms of suspected pneumonia.

2. Objective

The primary objective of this study is to estimate the impact of a self-monitoring tool (ChARM), used as a teaching/monitoring device, on the CHWs respiratory rate counting accuracy when assessing children under the age of 5 years with suspected pneumonia symptoms.

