- Intervention Group A: CHWs trained in ChARM and using ChARM as a self-monitoring tool for 8 months while counting respiratory rate of children under 5 visually using a timer.
- Intervention Group B: CHWs trained in ChARM and using ChARM as a self-monitoring tool for 4 months while counting respiratory rate of children under 5 visually using a time; then discontinue using ChARM and continue to monitor the respiratory rate visually using a timer only for the remaining 4 months.
- Control Group C: CHWs who did not receive the ChARM training and will be monitoring the respiratory rate of children under 5 visually using a timer only, as per the MoH traditional training.

Throughout the study 3 independent Field Monitors will follow each group's participants in both Banamba and Koulikoro (i.e. one Field Monitor will follow 1/2 CHWs in Group A in Banamba and 1/2 CHWs in Group A Koulikoro; the Field Monitors responsible for Groups B and C will also follow one study group each, in both areas). The Field Monitors will be responsible for both testing the accuracy of the CHWs' ability to count respiratory rate and for collecting data during the study from the CHW reports and drug records. The Field Monitors will receive the same training as the CHWs in the Intervention Groups A and B, and additional training on data collection and observation protocol. The Field Monitor will test the CHWs' capacity to count respiratory rate during three intervals:

[figure not shown]
- Before the ChARM training
- 4 months after initiating the use of the ChARM device
- 8 months after initiating the use of the ChARM device (which corresponds to 4 months after the ChARM device will be discontinued for group B).

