16.1. Field Monitors

The Field Monitors (described above) will be responsible to collect data at three different time periods, before the intervention, 4 months after the intervention begins and 8 months after the intervention begins. There will be one Field Monitor each for Groups A, B and C who will cover those groups in both districts. They will be practicing health

professionals and have participated in the 1-day ChARM training in which they will receive in-depth understanding of the required data collection forms and the ChARM device. Field Monitors will conduct 3 site visits to test the CHWs respiratory rate counting ability using a timer against the ChARM automated reading and record both readings. They will review and document the number of cases assessed for pneumonia, treated and/or referred by CHWs during the three testing periods.

Data Collection

i) Quantitative Data Collection:

Written informed consent will be taken from participating Community Health Workers in the Intervention and Control Groups, and from parents and caregivers of all children under five who will have their respiratory rates counted using the ChARM device. It will be made clear that eligible participants are under no obligation to participate in this study. In addition, the time burden associated with being involved in this study will be clearly outlined during the consent process.

Data from the CHW self-monitoring sheets filled out by Intervention Groups A and B will be reviewed and documented by the Field Monitor. The Field Monitor will also measure all CHWs respiratory rate counting capacity using ChARM as a global standard and collect routine CHW data three times during the study. This routine data is found in both the CHW monthly reports and the consultation/referral forms. Data from drug supply forms filled out by CHWs will also be collected to identify any variations that may occur due to more accurate pneumonia diagnosis by CHWs as a result of using ChARM and to triangulate this data with the consultation forms and other sections of the monthly report.

ii) Oualitative Data Collection:

Qualitative data collection will only take place in the intervention Groups A and B. Written, informed consent will be taken from CHWs, Field Monitors and MoH Technical Director of Health Centre (Directeur Technique du Centre/CSCom) participating in in-depth interviews. (Consent Forms - Annex 3, Questions for In-depth interviews - Annex 4).

Outcomes:

Primary outcome:

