Acute Respiratory Illness (ARI) Case fatality rate

Secondary outcomes:

Respiratory rate assessment accuracy

Proportion of pneumonia cases detected and treated by CHWs

Proportion of suspected severe pneumonia cases referred by CHWs to the CSCom

Proportion of suspected cases of pneumonia in the community who sought care from a CHW

Accuracy in drug management and procurement requests

Sample size:

48 clusters with average size of 50 suspected ARI cases per cluster per arm (over 8 months) are sufficient to detect a 30% reduction in the ARI case-fatality rate (from 20% at baseline), with 80% power and 5% significance. Differences in all secondary outcomes are powered above 80% within this sample size.

iCCM Curriculum Training: Intervention & Control sites

Participants: CHWs in Koulikoro and Banamba districts (n=148)

Time frame: Completed as part of CRC program implementation in Mali (December 2016 – August 2017)

Responsibility: CRC/MoH Mali Trainers

Training Material: Ministry of Health iCCM curriculum for CHWs -18-day curriculum including classroom instruction and hands on training.

Intervention Training: Intervention sites

Participants: CHWs in Koulikoro (n≅49) and Banamba (n≅49) districts.

Time Frame: After iCCM curriculum training; 9 months-1month for training CHWs in ChARM and 8 months for monitoring.

Responsibility: External Trainers and Study coordinator

- A. CHWs trained in ChARM and the self-monitoring data collection format.
- B. Submission of regular MoH monthly reports, consultation referral forms, drug supply forms.
- C. In-depth interviews for CHWs, Field Monitor and the Technical Director of Health Centres (Directeur Technique du Centre/CSCom) on their perception of ChARM tool and recommendations for future use as a teaching tool and/or scale up by the MoH.

Control Sites

CHWs in Koulikoro and Banamba districts (n=49)

Time frame: 8 months-including initial measurement of respiratory rate counts using a timer against ChARM's automated reading and subsequently repeating the measurement twice during the study.

- A. Pneumonia diagnosis as per usual practice of visually counting respiratory rate using a respiratory timer.
- B. Submission of regular monthly reports, consultation/referral reports and drug supply reports for review by Field Monitors.

12. Data Processing and analysis

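### The primary objective is counting accuracy, but the primary outcome is ARI case fatality, for which the protocol names no death source or follow-up; community care-seeking has no described denominator, and each arm has its own assessor

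*Protocol*

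**What the plan says.** **Objective and outcome.** The Project Summary and section 2 (Objective) set out to estimate the effect of ChARM "on the CHWs respiratory rate counting accuracy when assessing children under the age of 5 years with suspected pneumonia symptoms". The Project Summary and the Outcomes list in section 11 then name as primary outcome "Acute Respiratory Illness (ARI) Case fatality rate". Counting accuracy is listed as secondary.

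**Sample size (section 11).** 48 clusters per arm, averaging 50 suspected ARI cases each over 8 months, "are sufficient to detect a 30% reduction in the ARI case-fatality rate (from 20% at baseline), with 80% power and 5% significance".

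**Data sources.** Sections 6, 8, 9 and 11 name the self-monitoring sheets, CHW monthly reports, consultation/referral forms and drug supply forms. Section 16.1 says of the Field Monitors: "They will review and document the number of cases assessed for pneumonia, treated and/or referred by CHWs during the three testing periods". Section 6 (Phase I) likewise mentions cases treated or referred. Sections 8 and 9 say CHWs record respiratory rates, treatment and referrals. The Annex 1 list adds a monthly activity report and a referral and counter-referral form, whose contents are not reproduced.

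**Care-seeking.** A secondary outcome is "Proportion of suspected cases of pneumonia in the community who sought care from a CHW".

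**Assessors.** Section 16.1 assigns one Field Monitor to each group across both districts. Section 3 agrees: "the Field Monitors responsible for Groups B and C will also follow one study group each, in both areas". The same monitors test accuracy and collect data from the CHWs' reports and drug records.

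**The concern.** The outcome that sizes the trial does not answer the stated objective. Its numerator, deaths, has no named record, no time window and no described follow-up. A form completed at the consultation would not by itself show a later death at home or after referral. Missed deaths cost power. If capture differs by arm, which is plausible because ChARM is meant to influence whether a child is treated or referred, the comparison is biased.

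The care-seeking proportion needs suspected cases that did not reach a CHW, and none of the described sources can supply them.

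With one monitor per group, a difference between monitors in testing or abstraction cannot be told apart from a difference between arms.

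**Working it through.** **1. Outcomes against described sources**

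| Outcome | What it needs | What the text describes |
|---|---|---|
| ARI case fatality (primary) | Deaths; ARI cases | Cases assessed, treated, referred. Deaths not mentioned |
| Counting accuracy (secondary) | CHW count and reference reading | Both, all groups, at baseline, 4 and 8 months |
| Community care-seeking (secondary) | All suspected cases in the community | Only children who reached a CHW |

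The 2016 programme survey is cited as a reason for choosing sites. Figure II gives covered under-fives, not pneumonia cases.

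**2. The plan's own figure.** For 20% v 14%, two-sided 5% (sidedness assumed), 80% power:

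n = [1.96 √(2 × 0.17 × 0.83) + 0.8416 √(0.20 × 0.80 + 0.14 × 0.86)]² / 0.06² = 614.1, so 615 per arm without clustering.

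Planned: 48 × 50 = 2,400 per arm. Allowed design effect 2,400/615 = 3.90; implied ICC (3.90 − 1)/49 = 0.059. No ICC is stated. The 48 clusters are attainable at an ICC near 0.06.

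**3. Equal under-capture of deaths.** Recorded rates are the true rates times the captured fraction. Effective n = 2,400/(1 + 49 × ICC): 1,212 at ICC 0.02 and 609 at ICC 0.06. ICC and capture are assumptions.

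| Capture | Recorded rates | Power, ICC 0.02 | Power, ICC 0.06 |
|---|---|---|---|
| 100% | 20% v 14% | 97.6% | 79.7% |
| 75% | 15% v 10.5% | 91.4% | 65.4% |
| 50% | 10% v 7% | 75.5% | 46.7% |

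**4. Unequal capture.** Observed risk ratio = 0.70 × (ChARM capture/control capture). At 50% in control and 70% with ChARM it is 0.70 × 1.4 = 0.98. This shows the mechanism only; the documents give no capture figures.

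**5. Baseline rate.** The background states: "In Mali, about 900,000 pneumonia episodes occur in children under 5 years of age annually, leading to almost 8,000 deaths". That is 8,000/900,000 = 0.9%, giving 2,400 × 0.0089 = 21 control deaths against 15 after a 30% reduction, and 18.6% power without clustering. The same deaths over the 231,548 cases reported in 2013 give 3.5%, 83 v 58 deaths and 56.6% power, though this mixes sources and possibly years. The background also says that "case fatality rates can exceed 20" per cent.

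**6. One monitor per arm.** For an unadjusted two-arm comparison at one time point, in units of the CHW-level SD, SE = √(2/49) = 0.202. With between-monitor SD s, the true SD of the difference is √(0.202² + 2s²), and type I error is 2[1 − Φ(1.96 × 0.202/that SD)]. For assumed s = 0.1, 0.2 and 0.3 this gives 10.8%, 25.5% and 39.9%. In change from baseline a stable monitor effect cancels, so these figures do not carry over to a baseline-adjusted analysis.

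**7. Accuracy as primary.** With 148/3, or about 49, CHWs per arm and 80% power, a two-sample t test detects 0.57 SD at two-sided 5%, or 0.63 SD at 2.5% if alpha is split over two comparisons with control. This is before any gain from baseline adjustment.

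**8. Reassigning monitors.** Visits per monitor per round: 75/3 = 25 in Banamba and 73/3 = 24 in Koulikoro, against approximately 24 per district planned in section 3. Per group: 75/9 = 8.3 and 73/9 = 8.1 CHWs.

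**The case against.** **Unseen forms.** Annex 1 lists a monthly report, which is a periodic return and not a contact form, and a counter-referral form, whose title implies a return leg for referred children. Either may carry deaths. This stands. A reader might infer that deaths go unrecorded or that the primary outcome cannot be computed; the documents do not support that. They support only that the text names no source, window or follow-up.

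**Left to the SAP.** An SAP may define the analysis, but where deaths come from and whether children are followed are data-collection matters. The protocol describes its sources in detail without covering them.

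**Inflated error.** A reader might take 11–40% as the trial's type I error for accuracy. The protocol does not support that. All groups have a baseline test, a stable monitor effect cancels in change from baseline, and the automated reference limits judgement. What remains is drift over time and record abstraction, neither of which the baseline test removes. Section 4 makes the data collectors independent of delivery, but that does not separate monitor from arm.

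**Sponsor's choice of purpose.** Objective and outcome could be reconciled in either direction. This is fair, and the fix allows it.

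**Weakness of accuracy.** It is scored against the same device that gives Groups A and B feedback on each child, so part of any gain may be convergence to the device. This stands and must be disclosed.

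**Conclusion.** The concern holds as a mismatch between primary objective and primary outcome, a gap in the described death ascertainment, a secondary outcome with no described denominator, and avoidable confounding of assessor with arm. The first, third and fourth follow from the text itself. The second is a statement about the text, made without sight of the Annex 1 forms.

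The cost of missed deaths depends on assumptions. If half are captured, power is between 46.7% and 75.5% for ICC 0.06 to 0.02, under the protocol's 20% rate. A reader might also infer that the 48 clusters are miscalculated or that true power is about 19%. Neither is established. The 48 reproduces at an unstated ICC near 0.06, and the protocol's own background gives or implies rates from about 0.9% to above 20%. Those figures show that the 20% needs justification, not that it is wrong.

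**What to change.** 1. **Primary outcome.** Make counting accuracy primary, analysed with adjustment for the baseline test. Rewrite the sample-size paragraph for it, using the detectable differences in step 7. The protocol gives no SD, so the sponsor must justify that difference. State that the reference is the device that trains Groups A and B.
2. **Monitors.** Have each of the three existing monitors cover CHWs from all three groups, about 8 per group per district. Amend sections 3 and 16.1.
3. **Case fatality.** Report it as secondary, labelled *CHW-recorded deaths*, from a named form and item abstracted identically in all groups, with its incompleteness stated. If the sponsor keeps it primary, reconcile the objective to it and specify the death source and window.
4. **Care-seeking.** Drop the proportion, or replace it with cough/cold consultations per 1,000 covered under-fives per month, described as uptake, if site-level counts behind Figure II exist. For scale, (18,301 + 13,957)/148 = 218 covered children per CHW, and 50/(218 × 8) × 1,000 = 28.7 per 1,000 per month.

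**Cost.** Text changes and one named abstraction item; visits do not rise, but monitor schedules and travel must be rearranged. There is no confirmatory mortality claim, CHW-recorded deaths stay incomplete, and the uptake rate rests on 2016 denominators.

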The study is embedded in a 2016-2020 Maternal, Newborn and Child Health (MNCH) program in Mali funded by Global Affairs Canada; in partnership with the Malian and Canadian Red Cross Societies, the Mali Ministry of Health and the SickKids Centre for Global Child Health. The embedded nature of the study reduces project costs.

3. Trial Methodology and Sample Size

Methodology:

The study is designed as a community based, cluster randomized, pragmatic, intervention trial. It will be conducted within the existing 2016-2020 project structure. Specifically, the intervention will evaluate the potential of the ChARM device to improve CHWs competency in counting respiratory rate and diagnose pneumonia more accurately in children under 5 years presenting with symptoms in remote areas.

Sample Size:

Within the 2016-2020 Strengthening Maternal, Newborn and Child Health program 441 CHWs have been trained using the Ministry of Health curriculum to diagnose pneumonia in children under 5 by monitoring the respiratory rate visually using a timer. Counting respiratory rates visually using a timer is part of the MoH protocol for CHWs providing care to all children under 5 years of age seeking consultations presenting with symptoms of a cough and/or cold.

The study will be implemented in two (Banamba and Koulikoro) of the six districts the MNCH project is targeting. Of the 441 community health workers involved, 148 will participate in the study, 75 in Banamba and 73 in Koulikoro. This represents 34% of the 411 CHWs in the 2016-2020 program implementation area. **In each of the two** districts, 1/3 CHWs will be randomly assigned to intervention group A (monitoring the respiratory rate visually using a timer and the ChARM device for 8 months), 1/3 will be randomly assigned to intervention group B (monitoring the respiratory rate using both visual counting with a timer and the ChARM device for 4 months, followed by monitoring

the respiratory rate visually using a timer only for the next 4 months) and 1/3 of the CHWs will be assigned to group C (monitoring the respiratory rate visually using a timer only). This group will not be trained in ChARM nor use the device during the study). The CHWs will be randomly assigned to the following groups prior to the intervention.

Intervention and control groups are:

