At each of the three measures, the Field Monitor will test CHWs on their visual respiratory rate counting capacity using a timer against the ChARM automated readings and review supporting data sources. To maintain the study observation periods comparable, and save on the additional logistics costs, the intervention will be rolled out in Koulikoro 1 month after it has been rolled out in Banamba. Therefore, for the 2nd and 3rd direct observation the Field Monitors will begin first in Banamba and then one month later in Koulikoro. This will allow time for the Field Monitors to carry out the site visits required for each district for each of the measurements (approximately 24 visits per Field Monitor per district). As a result, the 2nd and 3rd measure for Groups A and B and C in Banamba will be at 4 months and 8 months, and the same groups in Koulikoro will be measured one month later, but still at 4 and 8 months.

The qualitative evaluation will be undertaken only in the Intervention Groups A and B using In-depth Interviews (IDIs) with CHWs, Field Monitors and the Technical Director of the Health centre responsible for the CHWs. In total 25 IDIs will be carried out. The Study Coordinator will be responsible for supporting the research and qualitative researcher who will be carrying out the IDIs. In total, anticipated number of IDIs are:

- Field Monitors 3 IDIs, one interview with each one
- Technical Director of Health Centre (Directeur Technique du Centre/CSCom) (DTCs) 10 IDIs (5 in Banamba and 5 in Koulikoro)
- Community Health Workers 12 IDIs

Figure I: RCT Flow Chart

4. Randomization

An epidemiologist not directly involved in the research project will perform randomization of clusters. Due to the nature of the intervention, blinding is not possible, however to ensure reduced measurement bias, data on the effect of the intervention will be collected by independent data collectors; not involved in the intervention delivery. The unit of randomization will be the community health worker.

5. Study Setting

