All CHWs in Groups A and B will use the both ChARM and visual breath counting using the timer for the first 4 months of the study. In the case of a discrepancy where there is enough variation that the CHW visual counts using a timer and the ChARM reading would put the child in different categories (i.e. rapid or non-rapid respiration) then the CHW will be instructed to use the ChARM reading for filling the section on the MoH form for Individual Case Management of a Sick Child (Fiche Individuelle de Prise en Charge de l'Enfant Malade – PEC) form. (Annex 1).

In the fifth month the Field Monitor will retest CHWs in Groups A and B, using the ChARM device as a global measure. The Field Monitor will also review the CHW monthly reports, PEC consultation/referral forms, drug supply forms, and the self-monitoring forms filled in by the CHWs.

For months 5 – 8, CHWs randomized to Group A will continue to use ChARM as a self-monitoring tool, continue to count respiratory rate visually using a timer and to compare and record the two measurements. Group B CHWs will discontinue using ChARM and only count respiratory rate visually using a timer. Both groups will continue to record the child's respiratory rates, treatment and referrals on the MoH forms they routinely fill out.

9. Control Group

All CHWS in the three groups received training on the basic CHW curriculum given by the Ministry of Health as off August 2017. In the training, they all received respiratory timers and were trained to count respiratory rate using those timers through classroom instruction, videos, and hands on practice in a health facility setting.

The control group (Group C) composed of 1/3 of the CHWs in Banamba and 1/3 of the CHWs in Koulikoro will have completed the basic MoH training, but will not receive the additional ChARM training or receive the device. Throughout the study Group C will count respiratory rate visually using a timer only and record the child's respiratory rates, treatment and referrals on the MoH forms they routinely fill out when assessing and treating a child presenting with symptoms of pneumonia. The Field Monitor for Group C in both districts will measure their breath counting competency, using the ChARM device as a global measure following the same testing intervals as the intervention groups A and B.

10. Study Trainers

The Intervention trainer for demonstrating how to count respiratory rates will be selected according to the following criteria:

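### The stated primary objective is counting accuracy, but the primary outcome and the only worked sample size are for ARI case fatality

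*Protocol*

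**What the plan says.** **Objective.** The Project Summary and Section 2 (Objective) give the same single primary objective: to estimate the effect of ChARM, "used as a teaching/monitoring device, on the CHWs respiratory rate counting accuracy when assessing children under the age of 5 years". The Methodology paragraph of Section 3 agrees, saying that "the intervention will evaluate the potential of the ChARM device to improve CHWs competency in counting respiratory rate and diagnose pneumonia more accurately". No stated objective mentions death.

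**Outcomes.** The Project Summary and the Outcomes list in Section 11 (Data Collection) name the primary outcome as "Acute Respiratory Illness (ARI) Case fatality rate". Accuracy comes first among five secondary outcomes, in Section 11 as "Respiratory rate assessment accuracy".

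**Sample size.** Section 11 says that 48 clusters per arm, averaging 50 suspected ARI cases each over 8 months, "are sufficient to detect a 30% reduction in the ARI case-fatality rate (from 20% at baseline), with 80% power and 5% significance". It adds: "Differences in all secondary outcomes are powered above 80% within this sample size". Section 3 also has a Sample Size heading, but gives only the number of CHWs available and their allocation.

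**Measurement.** Section 3 provides that at baseline, 4 months and 8 months "the Field Monitor will test CHWs on their visual respiratory rate counting capacity using a timer against the ChARM automated readings". This applies to all three groups.

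**The concern.** A primary outcome should answer the primary objective. Here fatality could show no difference while counting accuracy improved, or the reverse. In either case the formal primary test would say nothing about the question the Protocol says it asks.

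That question is left to a secondary outcome. With three groups and two follow-up tests there are several possible accuracy comparisons, and none is marked as the main one. The trial's answer could therefore be chosen after the data are seen.

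The accuracy data are not at risk, because they are collected in every arm at every test. What is at stake is which result counts as the trial's answer, and what the trial was sized to find.

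**Working it through.** **1. The statements side by side**

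| Place | Objective or purpose | Primary outcome | Rank of accuracy |
|---|---|---|---|
| Project Summary | Counting accuracy | ARI case fatality | Secondary |
| Section 2 | Counting accuracy | – | – |
| Section 3, Methodology | Counting competency, more accurate diagnosis | – | – |
| Section 11, Outcomes | – | ARI case fatality | Secondary |
| Section 11, Sample size | – | Inputs for fatality only | Power above 80% claimed, no inputs |

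The conflict stands in both the synopsis and the body, so it is not an isolated slip.

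**2. The Protocol's own figure**

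Inputs from Section 11: 20% against 20% × 0.7 = 14%, 80% power, 5% significance (taken as two-sided), 48 × 50 = 2,400 cases per arm.

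- Without clustering, the two-proportion formula with pooled variance under the null gives n = (1.960·√(2·0.17·0.83) + 0.842·√(0.20·0.80 + 0.14·0.86))² / 0.06² ≈ 615 per arm, or 13 clusters.
- The implied design effect is 2,400 / 615 = 3.90, so the implied intracluster correlation (ICC) is (3.90 − 1) / 49 ≈ 0.059.

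No ICC is stated, so 48 can only be solved backwards. It is attainable at a plausible ICC and is not shown to be wrong. But it is a calculation for fatality.

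**3. What an accuracy calculation would look like**

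The Protocol gives no metric, SD, control value or target difference, so no accuracy sample size can be derived from it. The figures below are conditional. They assume one continuous accuracy score per CHW, one two-arm contrast, two-sided 5% and 80% power. Arm sizes (about 49, 49 and 50) come from the Project Summary. The correlation r between baseline and follow-up scores is assumed.

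Detectable difference in SD units = (z for α + 0.842) · √(1/n₁ + 1/n₂) · √(1 − r²)

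- A vs C or B vs C: 2.802 · √(1/49 + 1/50) = 0.563 unadjusted.
- A and B pooled vs C: 2.802 · √(1/98 + 1/50) = 0.487 unadjusted.
- A vs C and B vs C as co-primary, Bonferroni at 0.025 each: (2.241 + 0.842) · 0.201 = 0.620 unadjusted.

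| Contrast | Unadjusted | r = 0.3 | r = 0.5 | r = 0.7 |
|---|---|---|---|---|
| A vs C or B vs C | 0.56 | 0.54 | 0.49 | 0.40 |
| A+B vs C at 4 months | 0.49 | 0.46 | 0.42 | 0.35 |
| Two co-primary contrasts | 0.62 | – | 0.54 | – |

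If accuracy were instead a yes/no result per CHW, with 49 per arm, the detectable absolute difference is about 22 to 28 percentage points for assumed control proportions between 30% and 70%.

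**4. Relevant only if fatality stays primary**

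The Background gives almost 8,000 deaths in about 900,000 episodes: 8,000 / 900,000 = 0.89%. It also says case fatality can be above 20%, so the two statements may use different denominators.

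- At 20%, 2,400 cases per arm give 480 deaths against 336.
- At 0.89%, they give about 21 against 15. Power for a 30% reduction is then 19% with no clustering, 14% at an assumed ICC of 0.01 and 8% at 0.05.

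**The case against.** **The text shows a disagreement, not which side is wrong.** Fatality is named primary twice and carries the only detailed calculation, and the Background links accurate diagnosis to survival. Restating the objective would remove the contradiction equally well. This stands as a legitimate second route. The preference for accuracy rests on the design: every Field Monitor test measures counting, and the contrast of 8 months' use, 4 months' use and none is suited to skill gain and retention.

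**Contrasts, covariates and multiplicity belong in a SAP.** The detail does, and its absence is not criticised here. Which question the trial answers, and what it was sized for, are protocol matters, and on these the Protocol contradicts itself.

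**The SD figures show no harm.** Agreed. They rest on assumptions outside the Protocol and do not disprove its claim of power above 80%.

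**Promoting accuracy is not free of difficulty.** Sections 3 and 11 assign one Field Monitor to each group, so assessor and arm are confounded, and Section 4 says blinding is not possible. Adjusting for baseline and district would not remove drift between monitors. The Protocol text also does not say how many children each CHW is tested on per visit. These points stand. They exist whichever outcome is primary and are not created by the realignment, but they would weigh more once accuracy is primary.

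**Conclusion.** The concern holds, and the inconsistency must be resolved. The primary outcome and the worked sample size address case fatality; the only stated objective addresses counting accuracy; nothing elsewhere in the Protocol reconciles them. This conclusion comes from the text and depends on no calculation. It does not require the 48 clusters to be wrong or accuracy to be underpowered.

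The conditional size of the gap is a detectable accuracy difference of about 0.35 to 0.62 SD, depending on contrast, multiplicity and the assumed baseline correlation, where the Protocol states nothing.

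**What to change.** Align the objective, primary outcome and sample size in the Project Summary, Section 2 and Section 11. The route that fits the data already planned is:

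1. Make counting accuracy the primary outcome (CHW timer count against ChARM reading, adjusted for the baseline test and district), with a one-line definition. Detail can go to the SAP.
2. Name one primary contrast and time point, and list the rest as secondary or adjust for multiplicity. The candidates are:
   - A+B vs C at 4 months, for the effect of use. Section 8 says "All CHWs in Groups A and B will use the both ChARM and visual breath counting using the timer for the first 4 months", so the two groups are treated alike until then and all 148 CHWs contribute.
   - A vs C at 8 months, for continued use.
   - B vs C at 8 months, for retention after stopping.
3. Move ARI case fatality to the secondary outcomes.
4. Replace the sample-size statement with the detectable difference for the chosen contrast, giving the assumed SD and baseline correlation.

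If the sponsor keeps fatality as primary, the objective should be restated as mortality. The Protocol should then confirm how deaths are ascertained in all three arms (the text names no method, but the annexed routine forms were not available to check) and reconcile the assumed 20% with the Background figures that give 0.89%.

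**Cost.** The realignment needs an amendment, ethics approval and a rewritten sample-size paragraph. It adds no CHWs, staff or visits, because accuracy is already tested in all arms at all three time points. Any change to the one-monitor-per-group arrangement would be a separate decision. Keeping fatality could cost far more if its true level is nearer 0.89%.
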